6.0 PRE-TREATMENT EVALUATION
(See Appendix I)

	Investigations	Timing
History and Physical Exam including:	
 history height/weight ECOG performance status vital signs: blood pressure & pulse clinical tumour / organomegaly measurements (if applicable) 	
Hematology	CBC, differential (including lymphocytes)	
Coagulation	PT, PTT	Within 7 days prior to registration
Biochemistry	
 creatinine potassium bilirubin (fractionated if known Gilbert's) AST, ALT alkaline phosphatase calcium albumin glucose (fasting) LDH B2 microglobulin HbA1c (if diabetic) 	
Radiology ¹	
 CT scan of neck, chest, abdomen and pelvis 	Within 21 days ² prior to registration
Mood Questionnaires ³	
 Patient self-rating mood scales for depression (PHQ-9) and anxiety (GAD-7)* 	Within 7 days prior to registration
Cardiac Investigations	
 12-lead ECG 	Within 7 days prior to registration
	
 MUGA/LVEF (only if symptoms suggestive or history of cardiovascular disease) 	Within 28 days prior to registration
Bone Marrow Studies	
 Bone marrow aspirate and biopsy for routine local pathology to assess CLL 	Within 28 days prior to registration
Other Investigations	
 Direct anti-globulin test (DAGT) 	Within 7 days prior to registration
	
 Serum or Urine Pregnancy test* (for women of childbearing potential) 	Within 7 days prior to registration
	
 Fluorescence in situ hybridization (FISH) for 17p and 11q deletion. Can be tested in bone marrow aspirate sample OR peripheral blood. Patient can be enrolled on trial before results are known. 	Within 28 days prior to registration
	
 Hepatitis B surface antigen (HBsAg) Hepatitis C serology 	
	
 Immunoglobulin variable region (IgV_H) mutation status. Can be tested on blood or bone marrow. Patient can be enrolled on trial before results are known. 	Any time prior to registration
Correlative blood work	
 Peripheral blood processed as per Section 17 and Laboratory Manual* 	Within 28 days prior to registration
Adverse Event ⁴	
 Baseline adverse event evaluation (to document residual adverse event from previous therapy and baseline symptoms) 	Within 7 days prior to registration

¹ To ensure comparability, baseline and subsequent CT scans to assess response must be performed using identical techniques (i.e. scans performed immediately following bolus contrast administration using a standard volume of contrast, the identical contrast agent, and preferably the same scanner).

² Twenty-eight days if negative.

³ Patient self-rating mood questionnaires (PHQ-9 and GAD-7) are posted on the IND 216 website.

⁴ Adverse events will be recorded and graded according to the NCI Common Terminology Criteria for Adverse Events (CTCAE) (Appendix V) with the exception of hematological and psychiatric toxicity which should be graded according to IW CLL guidelines (see Section 8.3).

* These tests are considered study-specific and must be performed AFTER the informed consent form has been signed.

7.0 ENTRY/REGISTRATION PROCEDURES

7.1 Entry Procedures

All registrations will be done through the CCTG web-based, password-operated Electronic Data Capture (EDC) system. Complete details regarding obtaining a password, accessing the system and registering patients will be provided at the time of study activation and will also be included in the “EDC Data Management Guidebook”, posted on the IND. 216 trial specific web-site. If sites experience difficulties accessing the system and/or registering patients, please contact the help desk (link in EDC) or the IND.216 Study Coordinator.

All eligible patients enrolled on the study by the participating treatment centre will be assigned a serial number which must be used on all documentation and correspondence with CCTG.

The following information will be required:

- trial code (CCTG IND.216)
- patient's initials (may be coded)
- informed consent version date, date signed by patient, name of person conducting consent discussion and date signed
- confirmation of the requirements listed in Section 5.0, including dates of essential tests and actual laboratory values
- height and weight

7.2 Registration

Registration will be provided electronically.

Note: All eligible patients admitted to the trial will be followed by the coordinating centre. It is the responsibility of the physician in charge to satisfy himself or herself that the patient is indeed eligible before requesting registration.

8.0 TREATMENT PLAN

Although the Canadian Cancer Trials Group acts as the coordinating agency for the trial, the responsibility for treatment of patients rests with the individual investigator.

In accordance with CCTG policy, protocol treatment is to begin within 2 working days of patient registration.

8.1 Chemotherapy Treatment Plan

8.1.1 Drug Administration

Agent	Route	Starting Dose	Frequency	Schedule
Buparlisib (BKM120)	oral	100 mg	Daily	Every 28 days

Safety will be reviewed after the first 3 patients are enrolled. If excess toxicity observed, starting dose will be reduced to 80 mg daily for subsequent patients. CCTG will advise.

A complete treatment cycle of buparlisib is defined as 28 days of once daily continuous treatment with a flat-fixed dose, i.e. not based on body weight or body surface area. There will be no breaks between dosing cycles.

The following general guidelines should be followed for buparlisib administration:

- Patients should be instructed to take the dose of buparlisib once daily in the morning, at approximately the same time each day.
- Buparlisib can be taken with or without food.
- Buparlisib should be taken with a glass of water. Patients should swallow the capsules whole and not chew them.
- If vomiting occurs during the course of treatment, no re-dosing of the patient is allowed before the next scheduled dose. The occurrence and frequency of any vomiting during a treatment cycle must be noted in the adverse events section of the eCRF.
- If the patient forgets and does not take their dose before 6:00 pm, then the dose should be withheld that day and buparlisib should be restarted the following day.
- Patients must avoid consumption of Seville orange (and juice), grapefruit or grapefruit juice, grapefruit hybrids, pummelos, starfruits and cranberry juice from 7 days prior to the first dose of study drug and during the entire study treatment period due to potential CYP3A interaction. Regular orange (*Citrus X sinensis*) juice is allowed.

8.1.2 Premedication

Routine anti-emetic premedication is not required but may be administered at the physician's discretion. Nausea and vomiting should be managed symptomatically if they arise. Non-steroid therapies are preferred since steroids may confuse the interpretation of response. Strong CYP3A inhibitors / inducers are prohibited and other CYP450 substrates should be used with caution (see Appendix VII).

Tumour lysis syndrome is uncommon in patients treated with buparlisib or idelalisib, an alternative PI3 kinase inhibitor. Investigators should follow standard local procedures for prophylaxis (e.g. hydration and allopurinol for those with high disease burden).

Buparlisib may cause lymphopenia thus prophylaxis with appropriate anti-microbial agents could be considered for patients at particular risk for serious viral infection or pneumocystis at the discretion of the investigator according to local protocols. Strong CYP3A inhibitors / inducers are prohibited and other CYP450 substrates should be used with caution (see Appendix VII).

Details of any premedication given must be properly recorded on the electronic CRFs.

8.2 Patient Self Rating Mood Questionnaires

The patient must complete two different mood questionnaires (PHQ-9 and GAD-7) on day 1 and day 14 in cycles 1 and 2, then day 1 each cycle, as well as the End of Treatment visit (Questionnaires are posted on the IND.216 website).

Instructions on how to instruct the patient to complete the questionnaires, as well as how to determine the scores will be provided together with each instrument.

8.3 Toxicity Grading

Adverse events will be graded using the NCI Common Terminology Criteria for Adverse Events (CTCAE) (see Appendix V) with the exception of hematological and mood questionnaires toxicity which should be graded according to IW CLL guidelines below. Guidance is also provided for interpretation of mood questionnaire scores.

Toxicity grading based on mood questionnaire scores:

PHQ-9 (Depression Score)			GAD-7 (Anxiety Score)		
Score	Severity	CTCAE grading	Score	Severity	CTCAE grading
0-4	None	Normal	0-4	None	Normal
5-9	Mild	Grade 1	5-9	Mild	Grade 1
10-19	Moderate	Grade 2	10-14	Moderate	Grade 2
20-27	Severe	Grade 3	≥ 15	Severe	Grade 3

Investigator assessment for suicidal ideation is required for any patient who does not answer Question #9 or the whole PHQ-9 questionnaire.

The grading guidance above may be overruled at the discretion of the provider performing a psychiatric consult.

Hematology toxicity grading based on IW CLL guidelines:

Grade*	Decrease in platelets** (nadir) from pre-treatment value	Decrease in Hb*** (nadir) from pre-treatment value	Absolute neutrophil**** count/ μ L (nadir)
0	No change to 10%	No change to 10%	≥ 2000
1	11 – 24%	11 – 24%	≥ 1500 and < 2000
2	25 – 49%	25 – 49%	≥ 1000 and < 1500
3	50 – 74%	50 – 74%	≥ 500 and < 1000
4	$\geq 75\%$ OR platelets < 20 at any time	$\geq 75\%$	< 500

* Grades: 1 mild, 2 moderate, 3 severe, 4 life-threatening, 5 fatal. Death occurring as a result of toxicity at any level of decrease from pre-treatment will be recorded as grade 5.

** Platelet counts must be below normal levels for grades 1 to 4. If at any level of decrease, the platelet count is $< 20 \times 10^9/L$, this will be considered grade 4 toxicity.

*** Hb levels must be below normal levels for grades 1 to 4. Baseline and subsequent Hb determinations must be performed before any given transfusions. In the event of red cell transfusion within 14 days prior to the baseline value, patient will be invaluable for Hb toxicity. The use of erythropoietin is irrelevant for the grading of toxicity but should be documented.

**** If the absolute neutrophil count (ANC) reaches $< 1 \times 10^9/L$, it should be judged to be grade 3 toxicity. Other decreases in the white blood cell count, or in circulating neutrophils, are not to be considered because a decrease in the white blood cell count is a desired therapeutic endpoint. A gradual decrease in granulocytes is not a reliable index in CLL for stepwise grading of toxicity. The use of growth factors such as G-CSF is not relevant to the grading of toxicity, but should be documented.

Grading scale for hematologic toxicity in CLL studies [Hallek 2008]

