8.4.1 Hematologic Toxicity

Worst Hematologic Toxicity*	Management
Grade 1 or 2	Maintain dose level
Grade 3 or 4 neutropenia Grade 3 thrombocytopenia	Omit dose until resolved to \leq grade 1 (or baseline) then: If resolved in \leq 7 days, then maintain dose level If resolved in $>$ 7 days, then decrease one dose level ***
Grade 4 thrombocytopenia	Omit dose until resolved to \leq grade 1 (or baseline) then decrease one dose level ***
Febrile neutropenia**	Omit dose until resolved to \leq grade 1 then decrease one dose level

* As defined according to IW CLL guidance in Section 8.3.
 ** ANC $< 1 \times 10^9/L$ with a single temperature of $\geq 38.3^\circ\text{C}$ or a sustained temperature of $\geq 38^\circ\text{C}$ for more than one hour.
 *** After treatment is resumed at a lower dose, if the same toxicity recurs with the same severity, then the next treatment should be resumed at a lower dose regardless of duration. If the same toxicity occurs with a worse severity, then the patient must discontinue treatment with buparlisib.
 If a third dose reduction is required, patients must discontinue protocol therapy.
 If therapy is delayed by $>$ 28 days, patients must discontinue protocol therapy.

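### In Section 8.3 the neutrophil column and its own footnote grade the same count differently, and Section 8.4.1 does not say which one decides when a hold ends or whether a recurrence is worse

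*Protocol*

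**What the plan says.** Protocol Section 8.3 introduces the scale as "Hematology toxicity grading based on IW CLL guidelines". In its neutrophil column, per µL, grade 1 is "≥ 1500 and < 2000", grade 2 is "≥ 1000 and < 1500", grade 3 is "≥ 500 and < 1000", and grade 4 is anything below 500.

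Footnote **** is attached to that same column. Of a count below 1 x 10^9/L (1000/µL) it says "it should be judged to be grade 3 toxicity". It continues "Other decreases in the white blood cell count, or in circulating neutrophils, are not to be considered", and then "A gradual decrease in granulocytes is not a reliable index in CLL for stepwise grading of toxicity".

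Section 8.4.1 takes its haematologic grades from 8.3 and uses them as follows:

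- Grade 1 or 2: dose unchanged.
- Grade 3 or 4 neutropenia (one shared row): drug withheld until the grade is 1 or lower, or baseline is regained. Recovery within 7 days keeps the dose; slower recovery costs one level.
- Febrile neutropenia: drug withheld until grade 1 or lower, with no baseline alternative, then one level lower.
- After a restart at a lower dose, a recurrence of the same severity leads to a further reduction. For a more severe one: "If the same toxicity occurs with a worse severity, then the patient must discontinue treatment with buparlisib".
- A delay of more than 28 days ends protocol therapy.

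Section 8.4 allows two reductions and no re-escalation. Section 14.3 reports each patient's worst event per category.

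**The concern.** The column grades stepwise, and its footnote says stepwise grading of falling granulocytes is unreliable in CLL. Taken literally, the footnote recognises one neutrophil grade where the column recognises four. Section 8.4.1 uses these grades to decide when drug may restart, whether the 7-day and 28-day limits have been passed, and whether a recurrence requires permanent discontinuation. Two sites following different halves of 8.3 could therefore treat the same blood counts differently, each with textual support. The neutropenia results for the safety objective (Section 1.2.1) would also depend on which half was used.

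**Working it through.** There is no stated figure to reproduce. The check grades the same counts both ways and carries the grades through 8.4.1. The footnote is read literally: below 1000/µL is grade 3, and anything else has no neutrophil grade.

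**Grades and immediate consequence** (1000/µL = 1.0 x 10^9/L)

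| ANC /µL | Column | Footnote, literal | Hold starts? | Low enough grade to end a hold? |
|---|---|---|---|---|
| 1800 | 1 | none | no under both | yes under both |
| 1500 | 1 | none | no under both | yes under both |
| 1200 | 2 | none | no under both | column no, footnote yes |
| 1000 | 2 | none | no under both | column no, footnote yes |
| 800 | 3 | 3 | yes under both | no under both |
| 400 | 4 | 3 | yes under both | no under both |

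The trigger is the same under both. The end of the hold differs only for 1000-1499, and only if baseline has not been regained.

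**(a) Release, 7-day test and 28-day limit.** These courses are illustrative, not trial data. Day 0 is the start of the hold.

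- Baseline 3.0; 0.9 on day 0, 1.2 on day 6, 1.5 on day 12. Column: 1.2 is grade 2 and below baseline, so the hold continues; 1.5 is grade 1 on day 12; 12 > 7, one level lower. Footnote: 1.2 carries no grade; 6 ≤ 7, same dose.
- Baseline 3.0; 0.8 on day 0, then 1.2 to 1.4 from day 7 to day 28, 1.6 on day 35. Column: 35 > 28, discontinue. Footnote: released on day 7, same dose.
- Control: baseline 1.2; 0.8 on day 0, 1.2 on day 5. Baseline is regained, so both release on day 5 at the same dose.
- Control: baseline 3.0; 0.8 on day 0, 1.6 on day 5. Both release on day 5 at the same dose.

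The febrile neutropenia row has no baseline alternative. Section 5.1.7 admits patients with ANC of 1.0 x 10^9/L or more. On the column, a patient with baseline 1.2 must reach 1.5, above that patient's own baseline, to restart; on the footnote, 1.0 is enough. The dose reduction in that row is unconditional, so only the restart date and the 28-day limit are affected.

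**(b) Severity of a recurrence.** This is a separate patient, because the rule applies only after a restart at a reduced dose. First episode 0.7, second episode 0.4. Column: grade 3, then grade 4, which is worse severity, so discontinue. Footnote: grade 3 both times, which is the same severity, so resume at a lower dose.

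**(c) Safety table.** On the literal footnote, a patient with nadir 0.4 is tabulated as grade 3 instead of 4, and one with nadir 1.2 is not tabulated instead of grade 2. Section 14.2 plans up to 29 patients overall and 12 in the PI3K inhibitor naïve cohort, so each regraded patient moves a frequency by 1/29 = 3.4 or 1/12 = 8.3 percentage points.

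**Is precedence set elsewhere?** Sections 6 and 9.1 and Appendix V refer haematologic grading back to 8.3. The tie-break in 8.4, which selects the lowest dose, covers several toxicities in one patient, not two grades for one count. The SAP gives no grading rule.

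**The case against.** The best defence is that 8.4.1 itself presupposes the column. It names grade 4 neutropenia and a return to grade 1, and only the column defines those grades. The footnote can then be read as marking the point at which neutropenia counts as severe, with the column splitting severe counts at 500. Its stated reason, that a falling white count is an aim of treatment, concerns scoring drug effect as toxicity rather than recovery after a hold. It also never says that 1000-1499 counts as resolved.

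Much of this stands. The restart level of 1000 and the absence of a grade 4 come from one literal reading. If the footnote means at least grade 3, the conflict in (b) disappears. But the footnote does not say so, and the 1000-1499 question in (a) would remain: the column calls such a count grade 2, and the footnote says it is not to be considered.

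A reader might go further and infer that the two halves disagree on when to start a hold. They do not: both start it below 1000, and 8.4.1 gives grades 3 and 4 the same action. Nor should (a) and (b) be joined into one patient's course. In the first course under (a) the footnote branch keeps the full dose, so the recurrence rule used in (b) would not yet apply.

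A reader might also infer an effect on the response rate, since Section 10.4 classifies best response only up to the end of treatment. The documents cannot support a size for that. Neutropenia is not among the most frequent toxicities listed in 8.4, and no frequency is given in the readable text.

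**Conclusion.** This is an internal contradiction in a rule that sites must apply, confined to neutrophils. It leaves the start of a hold unchanged. It affects the end of a hold, and so the 7-day and 28-day results, for counts of 1000-1499 still below baseline. It also affects the discontinuation rule for recurrences on either side of 500 after a reduced-dose restart, and the worst-grade neutropenia table. In the first illustrative course the two readings end the hold 12 - 6 = 6 days apart, and one of them uses one of the two permitted reductions.

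The conclusion rests on reading the footnote literally. Part (b) depends on that reading entirely; part (a) also needs a count the footnote disregards to be treated as resolved. The ANC courses are assumed, and the number of patients affected cannot be computed. The point merits correction because the text gives no way to choose between the readings, not because a large effect has been shown.

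**What to change.** The sponsor should reconcile the 8.3 neutrophil column, footnote **** and 8.4.1 so that one neutrophil grading applies. On that grading, the text should state:

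- how a count of 1000-1499 is treated for release from a hold, in both the neutropenia and febrile neutropenia rows;
- whether a count below 500 is worse severity than one of 500 to below 1000;
- that the safety tables under 14.3 use the same grading.

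This could be done by amending the column, amending the footnote, or clarifying what the footnote means. Which grading and which dosing rule apply is for the sponsor to decide.

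The cost is an edit to 8.3 and 8.4.1 and a line in the SAP. The counts are already collected, so neutropenia can be regraded by program. Dosing decisions already taken cannot be regraded. For patients already treated, the sponsor could list holds and discontinuations for neutropenia and record which reading each site used.

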8.4 Dose Adjustments

Dose Level	Daily dosing of buparlisib in 28 day cycle
-1	Reduce by 20 mg daily
-2	Reduce by 20 mg daily
-3	If required patients must discontinue protocol therapy

Doses will be reduced for hematologic and other adverse events considered related to buparlisib. Dose adjustments are to be made according to the system showing the greatest degree of toxicity.

The most frequently observed toxicities with buparlisib include transaminitis, skin toxicity, hyperglycemia, GI effects (diarrhea, anorexia, constipation, nausea, vomiting, mucositis), fatigue, abdominal pain and mood alterations.

The guidelines which follow outline buparlisib dose adjustments for several of these toxic effects. If a patient experiences several toxicities and there are conflicting recommendations, please use the recommended dose adjustment that reduces the dose to the lowest level.

Doses of buparlisib reduced for toxicity may not be re-escalated. For each patient, a maximum of 2 dose reductions will be allowed. Patients requiring an additional dose reduction will stop buparlisib and come off study.

Patients requiring a buparlisib dose delay of > 28 days must permanently discontinue buparlisib and come off study.

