8.4.2 Renal Toxicity

Worst Toxicity Serum creatinine	Management
Grade 1	Maintain dose level
Grade 2 ($> 1.5-3 \times$ baseline or ULN)	Omit dose until resolved to \leq grade 1 (or baseline) then: If resolved in \leq 7 days, then maintain dose level If resolved in $>$ 7 days, then decrease one dose level*
Grade 3 or 4 ($> 3 \times$ baseline or ULN)	Permanently discontinue buparlisib

* After treatment is resumed at a lower dose, if the same toxicity recurs with the same severity, then the next treatment should be resumed at a lower dose regardless of duration. If the same toxicity occurs with a worse severity, then the patient must discontinue treatment with buparlisib.
 If a third dose reduction is required, patients must discontinue protocol therapy.
 If therapy is delayed by $>$ 28 days, patients must discontinue protocol therapy.

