8.4.8 Other Non-Hematological Adverse Events, Including Diarrhea

Worst Toxicity	Management
Grade 1	Maintain dose level
Grade 2	Symptomatic management*; continue dosing with no change. For persistent grade 2 effects, investigator may decrease by one dose level
Grade 3 **	Omit dose*** until resolved to \leq grade 1 then decrease one dose level****
Grade 4	Permanently discontinue buparlisib

* For buparlisib induced diarrhea, standard treatment including prompt commencement of loperamide is recommended alongside rehydration (can refer to Recommended Guidelines for the Treatment of Cancer Treatment-Induced Diarrhea, [Benson 2004]).

** Omit for grade 3 nausea or vomiting only if it cannot be controlled with optimal anti-emetics.
Omit for fatigue only if significant worsening from baseline (investigator discretion).

*** Patients requiring treatment hold for >28 days will discontinue protocol therapy.

**** After treatment is resumed at a lower dose, if the same toxicity recurs with the same severity, then the next treatment should be resumed at a lower dose regardless of duration. If the same toxicity occurs with a worse severity, then the patient must discontinue treatment with buparlisib.

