9.3 Evaluation After Protocol Treatment

All patients will be seen 4 weeks after the end of the last cycle (4 Week Post Treatment Report).

Patients whose treatment is permanently discontinued due to an adverse event or non-hepatic clinically significant laboratory value, should be followed as clinically indicated until resolved to \leq grade 2. See Section 8.4.3 for more detailed guidance on patients who discontinue study treatment due to hepatic toxicity.

Follow-up beyond the 4 week treatment report is not required for patients who go off protocol treatment with progressive disease, except to document ongoing toxicities (until resolved to \leq grade 2), late toxicities (including second malignancies) and death if within 30 days of last dose.

For patients who go off protocol treatment with objective CR, PR or SD ongoing, follow up including response assessment will be required every three months until relapse/progression (Follow-Up Report). If the patient starts new anticancer therapy, contact the study coordinator to discuss whether further follow-up is required.

For patients who go off protocol therapy with suspected PR or CR, an 8 week confirmatory response assessment including CT scanning will be required as per Sections 9.1 and 10.4, if not already performed.

A Death Report is only required if death occurs within 30 days of last dose or if patient dies before progression/relapse; due within 2 weeks of knowledge of death (see Appendix IV –Documentation for Study).

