12.0 PROTOCOL TREATMENT DISCONTINUATION AND THERAPY AFTER STOPPING

12.1 Criteria for Discontinuing Protocol Treatment

Patients may stop protocol treatment in the following instances:

- Intercurrent illness which would, in the judgement of the investigator, affect assessments of clinical status to a significant degree, and require discontinuation of protocol therapy.
- Unacceptable toxicity as defined in Section 8.0.
- Progression or disease recurrence as defined in Section 10.0.
- Request by the patient.
- Completion of therapy as outlined in Section 8.0. Efforts should be made to maintain the investigations schedule and continue follow-up, even if patients discontinue protocol treatment prematurely and/or no longer attend the participating institution.

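### Section 8.4 takes patients *off study* at two kinds of toxicity stop, whereas Section 9.3 keeps those without progression in follow-up; the wording should be reconciled so that no site ends follow-up early

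*Protocol*

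**What the plan says.** **Dose-adjustment text.** Section 8.4 gives two triggers that end treatment for good. For a third reduction: "Patients requiring an additional dose reduction will stop buparlisib and come off study". For a dose delay of more than 28 days, patients "must permanently discontinue buparlisib and come off study".

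**The same triggers nearby.** The dose-level table in 8.4 says of the third reduction only that protocol therapy is discontinued. Section 8.4.1 says "If a third dose reduction is required, patients must discontinue protocol therapy" and treats the 28-day delay in the same way. Sections 8.4.2 to 8.4.7 do likewise for both triggers. Section 8.4.8 covers the delay: "Patients requiring treatment hold for >28 days will discontinue protocol therapy".

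**Other toxicity stops.** These do not mention leaving the study. For grade 3 or 4 renal toxicity, for example, 8.4.2 says only "Permanently discontinue buparlisib".

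**Follow-up text.** For patients who leave treatment with CR, PR or SD ongoing, Section 9.3 says "follow up including response assessment will be required every three months until relapse/progression". On unconfirmed responses it says: "For patients who go off protocol therapy with suspected PR or CR, an 8 week confirmatory response assessment including CT scanning will be required". It makes no exception for toxicity stops. After new anticancer therapy, further follow-up is discussed case by case. Section 12.4 refers to 9.3, and Appendix IV repeats both rules. Section 12.1 is softer: "Efforts should be made to maintain the investigations schedule and continue follow-up, even if patients discontinue protocol treatment prematurely".

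**Endpoints.** Sections 10.5 and 10.7 define response duration and PFS without a censoring rule. The SAP plans a median with range for response duration and a Kaplan-Meier plot for PFS, also without a censoring rule.

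**The concern.** In both sentences of 8.4, *off study* is a second step added to stopping the drug. Taken at face value it ends participation. For a patient with CR, PR or SD ongoing, that cannot stand beside a requirement for assessment every three months until progression.

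Three things are exposed if a site acts on 8.4 as written:

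- **PFS.** Follow-up would end at the stop, and the Kaplan-Meier curve would treat the patient as censored there. Patients who cannot tolerate treatment and are now untreated may have a different progression risk from those still on drug, so the censoring may be informative.
- **Response duration.** The end of the response would not be observed, and the SAP does not say how such a patient enters the median.
- **The primary endpoint.** CR and PR must be maintained for at least 8 weeks (Section 10.4). A patient who stops with an unconfirmed response could lose the assessment that confirms it.

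**Working it through.** **Step 1. One patient under each text.** Take a patient in PR whose dosing has been held for more than 28 days.

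| Place | Treatment | Follow-up |
|---|---|---|
| 8.4, text | stop | comes off study |
| 8.4.1 to 8.4.8 | stop | not mentioned |
| 9.3, 12.4, Appendix IV | already stopped | response assessment every 3 months to progression |
| 9.3, if the PR is unconfirmed | already stopped | 8-week confirmation including CT |
| 12.1 | already stopped | efforts to continue |

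Only the first row can be read as ending follow-up.

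**Step 2. What *off study* means elsewhere.** The only other use is in 12.2, for patients who progress. Section 9.3 still sees them at 4 weeks, but afterwards asks only for toxicity and early-death reporting. The term therefore does not end every assessment. In its one other use, though, it goes with the end of routine efficacy follow-up, so a site could reasonably take it that way.

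**Step 3. The plan's own figure.** Section 14.2 (PI3K-inhibitor-naive cohort) uses 5 then 12 evaluable patients, continues on at least 1 response and rejects at 2 or more.

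P(reject | p) = Σ over x = 1 to 5 of C(5,x) p^x (1−p)^(5−x) × P(Bin(7,p) ≥ max(0, 2−x))

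- p = 0.05: 0.2036 × 0.3017 + 0.0226 = 0.0840, within the stated 0.1.
- p = 0.30: 0.3601 × 0.9176 + 0.4718 = 0.8023, matching the stated 80%.

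The design reproduces. Its thresholds are small: if exactly 2 of 12 patients respond, or exactly 1 of the first 5, one lost confirmation reverses the decision. As an illustration, assume a share of true responders goes unconfirmed and counts as non-responders. Power at a true rate of 30% then becomes:

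| Assumed share unconfirmed | Effective rate | Power |
|---|---|---|
| 0 | 0.30 | 0.802 |
| 10% | 0.27 | 0.750 |
| 20% | 0.24 | 0.688 |
| 30% | 0.21 | 0.614 |

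**Step 4. PFS, illustration on assumed inputs only.** The documents give no expected PFS and no rate of toxicity stops. Assume an exponential PFS with an on-treatment median of 9 months, so λ = ln 2 / 9 = 0.0770 per month. Let a share q stop through the triggers by month 6, so μ = −ln(1−q)/6. If every such patient is lost at every site, the share of first progressions that falls after the stop is μ/(λ+μ).

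| Assumed q | μ | Share after the stop |
|---|---|---|
| 5% | 0.00855 | 10% |
| 10% | 0.01756 | 19% |
| 35% | 0.0718 | 48% |

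The last row is an upper illustration: it would need the literal reading to apply to a rate more like that of all toxicity stops.

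For the median, let the hazard after the stop be kλ. Then S(t) = exp(−(λ+μ)t) + μ exp(−kλt) [1 − exp(−(λ+μ−kλ)t)] / (λ+μ−kλ), and the median solves S(t) = 0.5. With censoring at the stop the curve would show 9.0 months in every case. At q = 10% and k = 2 the true median is 8.5 months. At q = 35% it is 7.5 months for k = 2, 9.0 for k = 1 and 10.0 for k = 0.67. The sign depends on k, about which the documents say nothing.

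**The case against.** The strongest reply is that this is loose terminology. Section 8.4 is about dosing, and nothing ranks it above the sections written for follow-up. Those sections agree: 9.0 requires every patient entered to be evaluated by the appendix schedules, and 9.3 explicitly contemplates patients stopped for an adverse event. Section 12.4 and Appendix IV point the same way. The dose-level table a few lines above the disputed sentences uses the treatment-only wording. PFS and response duration are secondary and descriptive, in at most 29 patients.

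Most of this stands. It makes continued follow-up the likeliest intent and lowers the severity. It does not make the two sentences correct: they are firm instructions to sites, while the nearest counterweight for premature stops, 12.1, asks only for efforts.

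A reader might go further and infer any of the following, none of which the documents support:

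- **That everyone who stops for toxicity leaves follow-up.** The phrase attaches to two triggers only. Grade 4 events, renal grade 3 or 4 and the other listed stops do not carry it.
- **That PFS is to be censored at a toxicity stop.** No such rule is stated. The loss would come from a misreading at a site, not from the planned analysis.
- **That about half of progressions would go unrecorded, or that the median is biased in a known direction.** The 48% rests on an assumed rate and on every site misreading 8.4.

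**Conclusion.** The wording conflict is real, confined to two sentences and two triggers, and of low severity. It matters for patients who reach a third reduction or a delay of more than 28 days with CR, PR or SD ongoing or with a suspected response, and only where the site takes 8.4 literally. For them, PFS and response-duration events could be lost in a way that may be related to prognosis, and a confirmation could be lost in a test that turns on 2 responses.

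The size cannot be derived from the documents. It depends on how often the two triggers occur, how sites read the phrase, and how progression risk changes after stopping. The figures in Step 4 and the power table in Step 3 show sensitivity under assumptions and do not estimate a bias. Section 12.2 is not part of the problem: its patients have already progressed, so their PFS and response-duration end dates are known.

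**What to change.** - **Protocol 8.4.** In both sentences, replace the closing phrase with *come off protocol treatment and continue follow-up per Section 9.3*. This reconciles 8.4 with its own table, its sub-sections, 9.3, 12.4 and Appendix IV.
- **SAP.** Add a line that PFS and response duration are not censored at the treatment stop itself.
- **Before analysis.** List any patient who stopped under either trigger and whose last response assessment falls at the stop, so that follow-up or a missing 8-week confirmation can be sought from the site.

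The cost is one phrase changed in two places at the next amendment, one SAP sentence and a short data listing. No dose or stopping criterion changes, no visits are added because 9.3 already requires them, and 12.2 can stay as it is.
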